#### **Adverse Reaction:**

All noxious and unintended responses to a medicinal product related to any dose should be considered adverse reactions (AR).

(The phrase "responses to a medicinal product" means that a causal relationship between a medicinal product and an AE is at least a reasonable possibility.)

The following additional definitions are being used by the Sponsor.

#### Solicited Adverse Events:

Solicited adverse events (AEs) are predefined signs and symptoms of reactogenicity for which the subject is specifically questioned, and which are noted by the subject in their Solicited Symptom Diary, including:

- fever (any temperature 100°F or higher)
- headache

- myalgia (muscle pain)
- abdominal pain
- anorexia (defined and not eating)
- nausea
- vomiting
- diarrhoea
- malaise/fatigue

Subjects will utilize a Solicited Symptom Diary issued on the day of the vaccination to record solicited any TEAE daily for the one week following that administration.

#### **Unsolicited AE:**

An unsolicited AE is an observed AE that does not fulfill the conditions prelisted in the eCRF in terms of diagnosis and/or onset window post-vaccination. Unsolicited AEs includes both serious (SAEs) and non-serious unsolicited AE.

Sentinel subjects will be kept at the site under observation for 2 hours after vaccination to ensure their safety. If there are no safety concerns during this period then randomized subjects will be kept under observation for 30 minutes after vaccination to ensure their safety. The post-vaccination observation period should be documented (including the actual time of observation) in the source document.

## 9.1.2 Grading of Severity of an Adverse Event

For adverse events (AEs) not included in the protocol defined grading system, the following guidelines will be used to describe severity:

- Mild Events require minimal or no treatment and do not interfere with the subject's daily activities.
- Moderate Events result in a low level of inconvenience or concern with the therapeutic measures. Moderate events may cause some interference with functioning.
- Severe Events interrupt a subject's usual daily activity and may require systemic drug therapy or other treatment. Severe events are usually potentially life-threatening or incapacitating. Of note, the term "severe" does not necessarily equate to "serious".

There are five principles that underpin the causality assessment for vaccine adverse events:

- 1. Biological plausibility
- 2. Temporal relation
- 3. Consistency
- 4. Specificity
- 5. Strength of association

For more details, refer to the causality assessment of an adverse event following immunization (AEFI): user manual for the revised who classification second edition, 2019 update link https://www.who.int/publications/i/item/9789241516990

All adverse events following immunization (AEFIs) must have their relationship to study drug assessed by the Investigator (clinician who examines and evaluates the subject based on temporal relationship and his/her clinical judgment). The degree of certainty about causality will be graded using the categories below. In a clinical trial, the study product must always be suspect.

- Definitely Related There is clear evidence to suggest a causal relationship, and other possible contributing factors can be ruled out. The clinical event, including an abnormal laboratory test result, occurs in a plausible time relationship to study drug administration and cannot be explained by concurrent disease or other drugs or chemicals. The response to withdrawal of the study drug should be clinically plausible.
- Probably Related There is evidence to suggest a causal relationship, and the influence of other factors is unlikely. The clinical event, including an abnormal laboratory test result, occurs within a reasonable time after administration of the study drug, is unlikely to be attributed to concurrent disease or other drugs or chemicals, and follows a clinically reasonable response on withdrawal.
- Potentially Related There is some evidence to suggest a causal relationship (e.g., the event occurred within a reasonable time after administration of the trial medication). However, other factors may have contributed to the event (e.g., the subject's clinical condition, other concomitant events). Although an AE may rate only as "possibly related" soon after discovery, it can be flagged as requiring more information and later be upgraded to "probably related" or "definitely related", as appropriate.
- Unlikely to be related A clinical event, including an abnormal laboratory test result, whose temporal relationship to study drug administration makes a causal relationship improbable (e.g., the event did not occur within a reasonable time after administration of the study drug) and in which other drugs or chemicals or underlying disease provides plausible explanations (e.g., the subject's clinical condition, other concomitant treatments).

• Not Related – The AE is completely independent of study drug administration, and/or evidence exists that the event is definitely related to another etiology. There must be an alternative, definitive etiology documented by the clinician.

## 9.1.4 Monitoring of Adverse Events during Trial

# 9.1.4.1 Monitoring of AE/SAEs from Day 1 to Day 29 after vaccination

Following AEs/SAEs, could appear during the entire course of the trial after vaccination. The following symptoms will be captured via Solicited Symptoms during Day 1 to Day 8. After Day 8 they will be captured as unsolicited adverse events. SAEs are captured from the first dose of study product.

- Fever/pyrexia
- Diarrhea
- Nausea
- Vomiting
- Abdominal pain
- Malaise/fatigue
- Anorexia
- Headache
- Myalgia (muscle pain)

# 9.1.5 Time Period and Frequency for Collecting AE, AESI, NOCIs, and SAE Information

All AEs AESIs and NOCIs will be collected from the first dose of study product until the follow-up visit at the timepoints specified in the SoA (Table 1).

Medical occurrences that begin before the start of study drug but after obtaining informed consent will be recorded as medical history/current medical conditions, not as AEs if it does not have a causal relationship with study participation. There are two situations to note as below.

- 1. If the medical occurrence causes the subject to be excluded from the study, then it must be reported by the investigator. This event will then need to be classified as an "AE not related to the study drug."
- 2. If the medical occurrence is the result of a protocol-specified intervention (prior to study drug dose), including but not limited to washout or discontinuation of usual therapy, diet, or a procedure then these must be reported appropriately as an AE (solicited and unsolicited), SAE, AESI, NOCI, and other reportable safety events by the Investigator.

All SAEs will be recorded and reported to the Sponsor or designee immediately and under no circumstance should this exceed 24 hours of being available. The Investigator will submit any updated SAE data to the Sponsor within 24 hours of it being available.

Investigators are not obligated to actively seek information on AEs or SAEs after conclusion of the study participation. However, if the Investigator learns of any SAE, including a death, at any time after a subject has been discharged from the study, and the Investigator considers the event to be reasonably related to the study drug or study participation, the Investigator must promptly notify the Sponsor.

# 9.1.6 Follow-up of AEs, AESIs, NOCIs and SAEs

After the initial AE/SAE report, the Investigator is required to proactively follow each subject at subsequent visits/contacts. All SAEs will be followed until resolution, stabilization, the event is otherwise explained, or the subject is lost to follow-up (as defined in Section 5.3).

The Investigator is obligated to perform or arrange for the conduct of supplemental measurements and evaluations as medically indicated to elucidate the nature and causality of the AE, AESIs, NOCIs or SAEs as fully as possible. This may include laboratory tests or investigations, histopathological examinations, or consultation with other health care professionals.

New or updated information will be recorded in the originally submitted documents.

The Investigator will submit any updated SAE data to the Sponsor within 24 hours of receipt of the information

# 9.1.7 Reporting of Adverse Event, Adverse Event of Special Interest, New Onset of Chronic Illness, Serious Adverse Events and Unanticipated problems

All AEs (solicited and unsolicited), AESIs, NOCIs SAEs and other reportable safety events that occur after the consent form is signed but before study product administration must be reported by the Investigator if the event cause the subject to be excluded from the study (these will be reported as "AE not related to the study drug") or is the result of a protocol-specified intervention, including but not limited to washout or discontinuation of usual therapy, diet, or a procedure.

Table 8 below summarizes the different reporting timelines for TEAEs (unsolicited and solicited), AESIs, NOCIs, SAEs, and SUSAR.

Type of Event	TEAE (unsolicited)	TEAE (solicited)	AESI/NOCIs	SAE / SUSAR
Reporting period	From first dose until 4 weeks after last dose of study drug	1 week after each study drug administration	From first dose until EOS	From first dose until EOS
Reporting Timelines to the Sponsor	Entered into the clinical database on an ongoing basis	Entered into the clinical database on an ongoing basis	Within 24 hours	Within 24 hours
Reporting Method	AE page of eCRF	Solicited Symptom Diary	AE page of eCRF	AE page of eCRF

#### Table 8 Adverse Event Reporting Timelines to the Sponsor

Abbreviations: AE = adverse event; eCRF = electronic Case Report Form; EOS = end of study; AESI = Adverse Event of Special Interest; NOCI= New Onset Chronic Illness; SAE = serious adverse event; SUSAR = suspected unexpected serious adverse reaction; TEAE = treatment-emergent adverse event

# **Adverse Event Reporting**

All subjects experiencing AEs after the first dose of study drug, until Day 29 (Active Period), whether considered causally related with the use of the investigational vaccine or not, must be monitored until symptoms subside, or until there is a satisfactory explanation for the changes observed, or until death, in which case a full pathologist's report should be supplied, if possible.

All findings must be reported on an adverse event page of eCRF and on the SAE form, if applicable. All findings in subjects experiencing AEs must also be documented in the subject's clinical research records.

The following information will be documented for each event:

- Reported term for the AE.
- Start and end date.
- Serious (Y/N)? If yes, appropriate seriousness criteria must be selected on eCRF and SAE Form.
- Severity.
- Investigator's opinion of the causality (relationship) between the event and administration of investigational vaccine(s) ("related" or "not related").
- Investigator's opinion of the causality (relationship) to trial procedure(s), including the details of the suspected procedure.
- Action taken with study treatment (investigational vaccine).,
- Outcome of event.
- For Death cases provide all applicable details (e.g. date and cause of death etc, including autopsy results if available).

#### **Serious Adverse Events Reporting**

The Investigator or designee will immediately report to the Sponsor any serious adverse event, whether or not considered study drug related, including those listed in the protocol or Investigator Brochure and must include an assessment of whether there is a reasonable possibility that the study drug caused the event. Study endpoints that are serious adverse events (e.g., all-cause mortality) must be reported in accordance with the protocol unless there is evidence suggesting a causal relationship between the study drug and the event (e.g., death from anaphylaxis). In that case, the Investigator must immediately report the event to the Sponsor.

All SAEs will be followed until satisfactory resolution or until the site Investigator deems the event to be chronic or the subject is stable. Other supporting documentation of the event may be requested by the Data Coordinating Center (DCC)/study Sponsor and should be provided as soon as possible.

The study Sponsor will be responsible for notifying the Food and Drug Administration (FDA of any unexpected fatal or life-threatening suspected adverse reaction as soon as possible, but in no case later than 7 calendar days after the Sponsor's initial receipt of the information. In addition, the Sponsor must notify FDA and all participating Investigators in an Investigational New Drug (IND safety report of potential serious risks, from clinical trials or any other source, as soon as possible, but in no case later than 15 calendar days after the Sponsor determines that the information qualifies for reporting.

All SAEs will be recorded and reported to the Sponsor or designee immediately and under no circumstance should this exceed 24 hours. The Investigator will submit any updated SAE data to the Sponsor within 24 hours of it being available.

#### 9.1.8 Pregnancy

Details of all pregnancies in female subjects will be collected after the start of study drug as per SoA (Table 1).

- If a pregnancy is reported, the Investigator will record pregnancy information on the appropriate form (pregnancy form) and submit it to the Sponsor within 24 hours of learning of the female subject or female partner of male subject (after obtaining the necessary signed informed consent from the female partner) pregnancy.
- While pregnancy itself is not considered to be an AE or SAE, any pregnancy complication or elective termination of a pregnancy for medical reasons will be reported as an AE or SAE.
- Abnormal pregnancy outcomes (eg, spontaneous abortion, fetal death, stillbirth, congenital anomalies, ectopic pregnancy) are considered SAEs and will be reported as such.

- The subject/pregnant female partner will be followed to determine the outcome of the pregnancy. If the subject/pregnant female partner (after consent is obtained to follow the pregnancy) delivers an infant, the subject/pregnant female partner and the infant will be followed up to one month post-delivery. The Investigator will collect follow-up information on the subject/pregnant female partner and the neonate and the information will be forwarded to the Sponsor.
- Any post study pregnancy-related SAE considered reasonably related to the study drug by the Investigator will be reported to the Sponsor. While the Investigator is not obligated to actively seek this information in former (study subjects/pregnant female partner) beyond the resolution of the pregnancy, he or she may learn of an SAE through spontaneous reporting.
- Any female subject who becomes pregnant while participating in the study will discontinue study drug or be withdrawn from the study may request continuation of study drug.

Should a female subject become pregnant during the course of the study after dosing, she will continue to be followed for safety and pregnancy outcomes. Subjects who have a positive pregnancy test at Day 1, prior to randomization, will be considered screen failures.

If a subject is found pregnant post study drug administration, the subject will only be monitored for safety.

# **Death Events**

Events resulting in death will be an SAE regardless of association to study drug. Death is an outcome and should not be reported as an event term. The event that leads to the death should be reported as the SAE term.

# 10. Safety Oversight

## **10.1 Internal Sponsor Review**

Safety data will be monitored on an ongoing basis by the Investigator (or medically qualified designee) and the Sponsor's Medical Monitor (or designee) in order to promptly identify and flag any event that potentially contributes to a Stopping Rule.

The lead Medical Monitor will be a physician experienced in the conduct of research clinical studies whose primary responsibility will be to monitor subject safety. The Medical Monitor will be responsible for reviewing the cumulative safety data, including a review of safety laboratory test results and adverse event reporting. The Medical Monitor will be familiar with study-specific data as well as relevant background information about the disease, investigational drug, and target population under study. The Medical Monitor(s) will be empowered to request a SMC safety review which can suspend the study, recommend amendments to the protocol, and/or to request further information.

## **10.2 Safety Monitoring Committee**

The first 10 sentinel subjects will receive open label high dose of active vaccine  $(2 \times 10^{11})$  in a staggered manner, no more than two (2) subjects dosed in a 24-hour period. All subjects dosed will be observed for a minimum of 2 hours post dose. While ten (10) subjects will be dosed in the sentinel group, to allow for dropouts, eight (8) subjects with complete safety data (defined as Day 1 to Day 8) will be enough to convene the SMC. If no dose-related toxicities are observed, and upon consideration of the SMC recommendations following review of safety data, enrollment of the randomized double-blind study will be initiated.

Alternatively, if pre-established stopping rules are met, enrollment of subsequent subjects will be halted until the study SMC has completed a review of all available safety data and offers a recommendation to proceed.

If any of the events described below are met during the overall conduct of the study (open label and randomized phase), the study will be halted, and no new randomization/vaccinations will be allowed pending an SMC safety review

- One or more subjects experiences a treatment-related serious adverse event (SAE) of any grade
- Two or more subjects experience the same treatment-related grade ≥3 solicited symptom within one week following vaccination.
- Two or more subjects experience the same treatment-related unsolicited grade ≥3 AE between Day 1 and Day 29 (Active Period).

The SMC will provide study oversight throughout the duration of the trial active and safety follow-up periods (Day 1 through Day 365 post-vaccination).

The IRB, US FDA-CBER will be notified if the study is halted for safety concerns.

A SMC will be created to provide oversight of the conduct of the trial to ensure the safety of subjects and the validity and integrity of study data. The committee will consist of independent physicians and/or scientists with vaccine clinical trials experience or expertise, and the Medical Monitor, who does not enroll subjects into the study. Please refer to the study specific SMC for details.

The SMC will function in accordance with the following provisions: (1) United States (US) Code of Federal Regulations (CFR) applicable to clinical studies (21 CFR Part 50, 21 CFR Part 54, 21 CFR Part 312.55 and 312.56. (2) ICH E6 and 62 Federal Register 25691 (1997): Good Clinical Practice (GCP) Consolidated Guideline.

Further details of the composition, pre-specified meetings and objectives of the SMC will be outlined in the SMC Charter.

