minutes after study drug administration for any acute reactions. Any acute reactions are to be recorded in the subject's source documents, on the AE page of the eCRF, and on a serious adverse event (SAE) form, as applicable. Subjects will be asked to record symptoms of reactogenicity daily for 1 week after study drug administration on Day 1, using the Solicited Symptom Diary; the Solicited Symptom Diary will be collected from the subject on Day 8 and reviewed.

- Subjects will be queried for unsolicited AEs for 28 days following the study drug administration and for SAEs, AESIs and NOCIs for 1 year following the study drug administration.
- Subjects will return to the site (as specified in SOA) and a blood, nasal and saliva samples will be collected for immunogenicity assessment.
- The subject will be asked to contact the site staff or Investigator if an AE (e.g., doctor's visit, emergency room visit) or hospitalization occurs.
- The subject is to be informed that use of prophylactic antipyretic/pain medication, while permitted, is not recommended on the day of study drug administration (before or after vaccination). If prophylactic antipyretic/pain medication is used, and if clinically appropriate in the judgement of the Investigator, acetaminophen is preferred over other non-steroidal anti-inflammatory drugs.
- Prior and concomitant medications will be reviewed if the subjects took any during the active study period.
- The subject will be asked to bring the completed Diary to the next visit.
- The subject will be reminded that study staff may contact them to obtain additional information on events entered into the Solicited Symptom Diary.
- Source documents will be completed.
- The Investigator or appropriately qualified designee will review the Diary data online following vaccination, to evaluate subject compliance and as part of the ongoing safety review. Daily review is optimal during the active Diary period. Any solicited symptom marked as Grade 3 should be specifically reviewed with the subject to ensure they meet the detailed solicited AE grading criteria in (Table 11) and evaluate for potential alternative etiology.
- An appointment will be scheduled for the subject to return for the next study visit.
- The Investigator or an authorized designee completes the eCRFs and an unblinded dispenser/administrator will update the investigational product accountability records.

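### The halting rules never add solicited and unsolicited cases of the same symptom, so one early and one late related grade ≥3 case trigger no automatic halt

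*Combined protocol and SAP*

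**What the plan says.** Section 10.2 lists three events that stop randomization and vaccination until the SMC has reviewed safety. They apply to the open-label and randomized phases alike.

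1. One related SAE, of any grade.
2. For diary symptoms: "Two or more subjects experience the same treatment-related grade ≥3 solicited symptom within one week following vaccination".
3. For other events: "Two or more subjects experience the same treatment-related unsolicited grade ≥3 AE between Day 1 and Day 29 (Active Period".

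Which of the last two rules counts an event depends on how it is recorded. Section 9.1.4.1 names nine symptoms (fever, diarrhea, nausea, vomiting, abdominal pain, malaise/fatigue, anorexia, headache, myalgia) that are solicited from Day 1 to Day 8. Of the same symptoms later on it says: "After Day 8 they will be captured as unsolicited adverse events". Section 9.1.1 agrees, defining an unsolicited AE as one "that does not fulfill the conditions prelisted in the eCRF in terms of diagnosis and/or onset window post-vaccination".

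There are also discretionary safeguards. Section 10.1 has the Investigator and Medical Monitor watch the data "in order to promptly identify and flag any event that potentially contributes to a Stopping Rule", and adds: "The Medical Monitor(s) will be empowered to request a SMC safety review which can suspend the study". Section 7.1.2 adds a check of severe diary entries: "Any solicited symptom marked as Grade 3 should be specifically reviewed with the subject".

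**The concern.** By the protocol's own standard, a second like related grade ≥3 event is enough to stop dosing without anyone having to exercise judgment. For the nine listed symptoms that standard lapses when the two cases fall on either side of Day 8, because each count then stands at one. An unlisted event on the same two days would meet the third rule. The symptoms the protocol expects (Section 2.4.1) thus get slightly weaker protection than unexpected ones. The documents give no reason for this, and it looks like a side effect of how data are captured.

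At stake is whether further healthy volunteers are dosed between the second and third severe case without a mandatory review.

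**Working it through.** The plan gives no operating characteristics for the halting rules, so there is no stated figure to reproduce.

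**Which patterns are missed.** Take one listed symptom and consider only related, non-serious grade ≥3 cases. Let S be the number of subjects with a case in Days 1-8 and U the number with a case in Days 9-29. The automatic halt requires S ≥ 2 or U ≥ 2. Enumerating every combination for 2 to 5 subjects leaves exactly one pattern with at least two affected subjects and no halt: S = 1 and U = 1, in different subjects. A third affected subject must raise S or U to 2. If the first subject's symptom recurs after Day 8 as a new related event, U reaches 2 and the study halts with only two subjects affected. Serious cases fall outside the gap, since one related SAE halts the study. In Table 11, grade 3 diarrhea (for example 6 or more watery stools) need not be serious.

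**How likely the pattern is.** Inputs: n = 50 + 50 + 10 = 110 vaccinees (Table 3). The per-subject risks p (Days 1-8) and q (Days 9-29) are assumptions; subjects are independent, and each has an early case, a late case or neither.

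- Missed pattern: n(n−1)·p·q·(1−p−q)^(n−2)
- p = 0.5%, q = 0.05%: 110 × 109 × 0.005 × 0.0005 × 0.9945^108 = 0.0165
- p = 0.5%, q = 0.1%: 110 × 109 × 0.005 × 0.001 × 0.994^108 = 0.0313

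With r = p + q, a pooled rule triggers with probability 1 − (1−r)^n − n·r·(1−r)^(n−1). The present separate rules trigger with that probability less the missed pattern.

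| Assumed p / q | Separate rules | Missed pattern | Pooled rule |
|---|---|---|---|
| 0.5% / 0.05% | 0.107 | 0.0165 | 0.123 |
| 0.5% / 0.1% | 0.110 | 0.0313 | 0.142 |

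The answer moves with the rates. At 0.1% / 0.01% the same formula gives 0.11%. At 1% / 0.5%, letting one subject have both kinds of case, it is 11.6%; over a grid of higher rates (p 0.5% to 3%, q 0.2% to 1%) it runs from about 4% to 13%. At q = 0 it is zero. The only specific evidence in the protocol is the monovalent boost study in Section 2.2.3, which had no severe solicited symptoms and no related unsolicited AEs.

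**How often a halt would still spare someone a dose.** Two million early/late pairs were simulated under further assumptions: sentinels dosed two per day, randomized dosing starting 7 days after the last sentinel's Day 8, even enrollment, and event days uniform within each window. The share column counts missed patterns that are complete before the last vaccinee is dosed and whose early case is not a sentinel, as a fraction of all missed patterns. Sentinel early cases are left out because they already face SMC review before randomized enrollment.

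| Enrollment period | Share | × 0.0165 | × 0.0313 | Median vaccinees still undosed |
|---|---|---|---|---|
| 4 weeks | 0.330 | 0.5% | 1.0% | 19 |
| 8 weeks | 0.599 | 1.0% | 1.9% | 25 |
| 12 weeks | 0.695 | 1.1% | 2.2% | 27 |

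A 14-day gap before randomized dosing leaves the shares essentially unchanged (0.331, 0.599, 0.696).

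**The case against.** The strongest reply is that the second case would not go unseen. Contributing events must be flagged. The Medical Monitor sits on the SMC (Section 10.2), which oversees safety through Day 365 and may look at unblinded data (Section 6.7.2). Subjects with severe events are told to contact the site (Section 8), the sponsor runs continuous signal detection (Section 14.1), and the trial can be suspended at any time (Section 4.5). For sentinels, Section 10.2 sets a stricter condition for going on: "If no dose-related toxicities are observed, and upon consideration of the SMC recommendations following review of safety data". All of this stands, and it limits the consequence. But outside the sentinel stage each route to a pause depends on someone's judgment, whereas the three listed events oblige a halt.

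Separate counting can also be defended on its merits. The second rule is a first-week reactogenicity rule, and a Day 5 and a Day 12 case need not be one signal. That is fair, and some pooled pauses would join unrelated cases. Both cases must, however, be judged related, and the third rule already joins Day 5 and Day 12 cases of any unlisted event.

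Three further points stand. Some grade 3 cases may be judged medically important, hence serious, and halt the study after one subject. The probabilities rest wholly on assumed rates and an assumed enrollment pace. And the SMC Charter may already pool the counts.

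**Conclusion.** The gap is real and narrow. For a listed symptom, exactly one related, non-serious grade ≥3 case in Days 1-8 plus exactly one in another subject in Days 9-29 meets none of the automatic rules. At most, the mandatory halt moves from the second affected subject to the third; until then a pause is at the Medical Monitor's, SMC's or sponsor's discretion.

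On the assumed rates of 0.5% early and 0.05% to 0.1% late, the pattern has a 1.7% to 3.1% chance per symptom. The part in which a halt could still prevent a vaccination, sentinel early cases aside, is about 0.5% to 2.2%. The logical finding needs no assumed rates; its size does. This is a cheap improvement of low priority, held with medium confidence because the Charter could not be checked.

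**What to change.** Add one sentence to Section 10.2 and mirror it in the SMC Charter, for example: *For symptoms listed in Section 9.1.4.1, subjects with the same treatment-related grade ≥3 symptom are counted together from Day 1 to Day 29, whether it is recorded as solicited or unsolicited.* The two-subject and grade ≥3 thresholds stay as they are, and no new data or visits are needed.

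The cost is the extra chance of a pause for SMC review: 1.6 percentage points per symptom (12.3% against 10.7%) or 3.2 points (14.2% against 11.0%) at the two assumed pairs of rates. The rules count subjects rather than vaccinees and relatedness is judged blind, so placebo cases can count too. With all 135 subjects at the same rates, the figures become 17.1% against 14.9%, and 19.5% against 15.4%. Nine symptoms are listed, so the chance of a pause for any of them is higher.
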